## **1. Participant Group**

This study uses a two-period crossover design in which Group A and Group B alternate between an intervention and a non-intervention period over 24 weeks.

Group A will self-administer Neuro-World cognitive training games for 30 minutes per day, twice a week, for 12 weeks in a home setting (intervention period). This will be followed by 12 weeks without any therapist-supervised cognitive therapies (non-intervention period).

Group B will first complete a 12-week non-intervention period without therapist-supervised cognitive therapies. This will be followed by 12 weeks of self-administered Neuro-World cognitive training games for 30 minutes per day, twice a week, in a home setting (intervention period).

## **2. Statistical Analysis Plan**

Paired t-tests will be conducted to evaluate changes in outcome measures between the intervention and non-intervention periods. The outcome measures include the Montreal Cognitive Assessment (MoCA), Mini-Mental State Examination (MMSE), Digit Forward Span (DFS), Digit Backward Span (DBS), Geriatric Depression Scale (GDS), SF-36 Mental Component Summary (MCS) Score, and the Lawton-Brody Instrumental Activities of Daily Living (IADL) Scale. The null hypothesis is that the intervention results in no improvement or worse outcomes compared to the non-intervention period. The alternative hypothesis is that the intervention leads to improved outcomes. All analyses will be conducted using Python, with a one-sided significance level of 0.05.

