- When the UMass RA finds a study ID with the completed **Informed Consent instrument** (i.e., green color), the RA refers to **random_group_assign.xlsx** (in the Google folder **Pre-determined randomization, which is only available to the UMass RAs**) and assigns the study ID to either Group A or B.

- **Group A**
 - First period: Neuro-World game intervention (12 weeks)
 - Second period: phone interaction + usual care (12 weeks)
- **Group B**
 - First period: phone interaction + usual care (12 weeks)
 - Second period: Neuro-World game intervention (12 weeks)

- **The Randomization instrument** will be hidden from the Rutgers personnel throughout the study.

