- Group B: “OK. I will give the overall process of our study first. Our study participants are divided randomly into Group A/B. You are selected as Group B. It means that For the first 12 weeks, you don’t need to do anything for this study but we will just check you about your cognitive and physical activity such as puzzles, board games or hiking like that. After 12 weeks, you will receive a table PC and play a cognitive training game. For this assessment, an important note is that [name] should not know about which group you are in. *Please know that [name3] is only here for the assessment purpose. To assess your cognitive function without any bias, [Rutgers RA] should not know that you are starting 12 weeks with no game play and you will receive a table PC 12 weeks later. So, if you have any concerns or questions related to our overall study procedure, game play or tablet PC, please feel free to talk to me or ask me. {(optional) For today's assessment, [Helper Name] will be asked survey questions related to [participant name]'s daily activity first before starting cognitive assessment. I will break a zoom room for [participant name] during the survey, and let [participant name] join again after completing the survey. [participant name], do you feel comfortable with using zoom? After completing the survey, [helper name] please stay in the house but not in the room during the assessments.} The entire assessment will be video-recorded for future reference. Now the [Rutgers RA] will join and start the assessment. I will stay muted until the assessment is over; but if you have a question, please feel free ask to me.”*”
-
- The UMass RA will bring the Rutgers RA back to the main meeting room and start **recording the assessment**.
- Five different **Assessment Form (1-5) instruments** have a different randomized order of tests. RAs select an assessment form using **Assessment/Assessment Form Assignment.xlsx** in Google drive. Then, the questions and fields of the selected **Assessment Form instrument** will appear.
- The Rutgers RA will administer all the assessments and enter all answers to **the corresponding Assessment Form instrument**. The Rutgers RA will score the participant as he/she administers the assessments.

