 - In the past two days, did you do any PHYSICAL activities or exercise such as going for a walk, biking, swimming, exercise videos/classes or anything else you can think of?
 - If yes, how long?
- For the caregiver (optional),
 - During this week, did you meet the participant?
 - In the past two days, did you see the participant do any COGNITIVE activities such as Sudoku, board games, word games, or any other activities you do to help your memory and mental capacity?
 - If yes, how long?
 - In the past two days, did you see the participant do any PHYSICAL activities or exercise such as going for a walk, biking, swimming, exercise videos/classes or anything else you can think of?
 - If yes, how long?

9. Assessment after 12 weeks (Only Rutgers RA can perform assessment; UMass RAs will organize the overall meeting)

- After 12 weeks, all participants will be assessed with the following tests **online (via zoom)**.

Detailed steps will be the same as the baseline assessment.

RAs will generate a new form for recording 12 weeks follow-up assessment from the corresponding Assessment Form instrument.

10. Returning tablet PC (UMass RAs will perform)

- A UMass RA will track the returning delivery of the tablet computer.
 - The UMass RA should have instructed the participant or the caregiver to return the tablet computer. If not,
 - Call the participant or the caregiver to provide the instructions. (Refer to **8. Checking compliance every week**)
 - The UMass RA, who is on the designed days, will check the tracking number based on **the Tracking number field (Returning to the UMass from the subject) of the Tablet Ship & Return instrument**. The following is an example.
 - UMass RA1: Wed
 - UMass RA2: Fri
 - If the returning package has been picked up by the UPS,
 - Enter the date in **the Shipped date field of the Tablet Ship & Return instrument**.
 - If the returning package is shown delivered,
 - The RA will retrieve the tablet computer.
 - The RA will check if both the tablet computer and the charger are included in the box.
 - If the returning package is shown delivered but the package is not delivered,
 - The RA will contact the UPS and file a claim.

11. Interview (UMass RAs will perform)

- A UMass RA will remind the participant and the caregiver of the scheduled interview.
 - Give a call to the participant and the caregiver, remind them 1 day before the scheduled interview in the following order.
 - Phone call
 - If not answering, text and email.

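### Paired t-tests alone, in a crossover with no washout, give an effect that depends on how much of Group A's training gain persists; the pair is undefined, period is ignored and the randomised week-12 comparison is missing

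*SAP*

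**What the plan says.** SAP section 1 sets out the design: "This study uses a two-period crossover design in which Group A and Group B alternate between an intervention and a non-intervention period over 24 weeks". Training comes first for Group A; then "This will be followed by 12 weeks without any therapist-supervised cognitive therapies (non-intervention period". Protocol section 4 gives Group A the same order: "Second period: phone interaction + usual care (12 weeks". Neither document places a gap between the periods or mentions carryover or retention.

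Everyone is assessed at baseline, week 12 and week 24. Protocol section 9 says "After 12 weeks, all participants will be assessed with the following tests", and section 12 does the same for week 24. Week 12 is therefore both the end of period 1 and the only starting value for period 2. Of the five assessment forms, Protocol section 5 says that they "have a different randomized order of tests"; it mentions no alternate versions of the tests.

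The analysis in SAP section 2 is: "Paired t-tests will be conducted to evaluate changes in outcome measures between the intervention and non-intervention periods". The test is one-sided: "The null hypothesis is that the intervention results in no improvement or worse outcomes compared to the non-intervention period", and "All analyses will be conducted using Python, with a one-sided significance level of 0.05". The supplied text names no period or sequence term, no carryover assumption and no comparison of Group A with Group B. Some SAP text before section 1 was not available, but section 2, the analysis section, was.

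**The concern.** A paired t-test on pooled participants treats the control period as a clean reference. For Group B it is one. For Group A it is not, because the control period begins where training ended. If the gain fades, Group A's control change is negative and enlarges a contrast of changes. If the gain lasts, Group A's two end-of-period scores are alike and a contrast of end scores shrinks. The SAP sentence allows either contrast, and they are unbiased at opposite extremes of retention.

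A second, smaller issue is separate from carryover. The same battery is given three times, so practice or decline over time is plausible. A period effect enters the two groups with opposite signs, and the paired test has no term to remove it.

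At stake is the meaning of the trial's effect for all seven outcomes. The one contrast that avoids both problems, Group A against Group B at week 12, is not planned.

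**Working it through.** The documents give no effect size, SD, correlation or power, so there is no design figure to reproduce.

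**Inputs from the documents.** 50 participants (Protocol section 1), visits at weeks 0, 12 and 24, one-sided 0.05 (SAP section 2).

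**Assumptions.** Both groups are pooled, which is the natural reading but is not stated. The allocation ratio is not stated, so 25/25 is the base case. For simulation: SD 2.5, correlation ρ = 0.7 between any two visits, d = 1.25, 40,000 runs per setting.

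**Expected scores.** Let p1 and p2 be the changes over periods 1 and 2 that are unrelated to training.
- Group A: 0, p1 + d, p1 + p2 + rd
- Group B: 0, p1, p1 + p2 + d

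**Training minus control, on within-period changes.**
- Group A, 2·Y12 − Y0 − Y24: (p1 − p2) + (2 − r)d
- Group B, Y24 + Y0 − 2·Y12: (p2 − p1) + d
- Mean with equal groups: (3 − r)/2 × d

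**Training minus control, on end-of-period scores.**
- Group A, Y12 − Y24: −p2 + (1 − r)d
- Group B, Y24 − Y12: p2 + d
- Mean with equal groups: (2 − r)/2 × d

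The two readings always differ by 0.5d. This is algebra and does not depend on the assumed SD or correlation.

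**Estimate and power, d = 1.25, 25/25, no period effect.**

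| r | Changes | End-of-period | Week-12 ANCOVA |
|---|---|---|---|
| 0 | 1.88 (99%) | 1.25 (99.8%) | 1.25 (78%) |
| 0.5 | 1.56 (94%) | 0.94 (95.5%) | 1.25 (78%) |
| 1 | 1.25 (83%) | 0.63 (70%) | 1.25 (78%) |

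Adding a period term leaves the paired estimates unchanged, so it does not cure carryover.

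**Period effect when training does nothing (d = 0).** The pooled mean is biased by (nA − nB)/N × (p1 − p2) on changes and by (nB − nA)/N × p2 on end-of-period scores. For a 1-point period difference this is 0 at 25/25, 4/50 = 0.08 at 27/23 and 10/50 = 0.20 at 30/20, in either direction. One-sided type I error:

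| Split | Changes | End-of-period |
|---|---|---|
| 25/25 | 4.2–4.4% | 3.3% |
| 27/23, larger group favoured | 6.0% | 5.8% |
| 30/20, larger group favoured | 9.5% | 13.1% |
| 27/23, smaller group favoured | 2.9% | 1.6% |
| 30/20, smaller group favoured | 1.7% | 0.6% |

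The favoured group is the one that trains in the better period. For a gain from week 12 to week 24 only, that is B on both readings. For a gain by week 12 only, it is A on changes, and end-of-period scores are unaffected. With a period term the error is 4.8–5.1% throughout.

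**Standard errors, N = 50.**
- Changes: √(6 × 2.5² × 0.3 / 50) = 0.474
- End-of-period: √(2 × 2.5² × 0.3 / 50) = 0.274
- Week-12 ANCOVA: √(4 × 2.5² × (1 − 0.7²) / 50) = 0.505

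**The case against.** The strongest reply has five parts.

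- **The test stays valid in the base case.** If training has no effect there is nothing to carry over, and with equal groups an ignored period effect only makes the test conservative. Section 2 describes a hypothesis test and promises no point estimate. This stands, so the concern rests on effect size and power. It still matters, because a significant result will be reported with a size and the plan leaves that size undefined.
- **Inflated error needs assumed inputs.** It requires unequal groups and a period effect. At 27/23 the excess is about one percentage point. With equal practice gains in both periods the change reading is unaffected even at 30/20. A MoCA score is already taken at screening, which may use up some practice gain before baseline. This stands: the splits and the 1-point effect are illustrative.
- **A period or sequence term cannot supply r.** Correct. In this design a sequence effect cannot be separated from carryover, and the paired difference already removes constant differences between groups. The missing period term is a secondary fault.
- **The change reading is the more natural one.** Perhaps, but it still ranges from 1.0d to 1.5d, and the choice should not be open once data are seen.
- **Week-12 ANCOVA usually has less power.** True here: 78%, against 83–99% on changes. It is ahead only of end-of-period scores near full retention. That argues for care in making it primary, not for leaving it out.

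**Conclusion.** The concern holds and must be fixed. As written, the analysis returns d only if Group A's gain is fully kept (change reading) or fully lost (end-of-period reading). Anywhere between, the first overstates d, by up to half, and the second understates it, by up to half. These multiples assume pooled, equal groups and nothing else. The power and error rates also rest on the assumed SD, correlation, effect and splits. Carryover distorts size and power, not the error rate under a strict null. Leaving out period is the lesser fault: conservative with equal groups, biased in either direction with unequal ones.

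**What to change.** 1. **Define the analysed quantity.** State whether it is the within-period change or the end-of-period score, and that both groups are analysed together.
2. **Replace the paired t-test with a crossover analysis.** Either compare within-person period differences between the two sequence groups, or fit a mixed model with treatment, period and sequence using all available visits. State the retention assumption it needs: r = 1 for changes, r = 0 for end-of-period scores.
3. **Add the randomised comparison of Groups A and B at week 12**, by ANCOVA on the baseline score, as the carryover-free estimate. State its role relative to item 2.

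These items need SAP wording and a few lines of Python. The period term costs one degree of freedom, and the week-12 comparison uses data already scheduled for everyone.

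Making week 12 primary is an option with a real price. Its variance is (2/3)(1 + ρ) times that of the change contrast, or 1.0 to 1.2 times for ρ from 0.5 to 0.8. Against the end-of-period contrast it is 2(1 + ρ), or 3.0 to 3.6 times. The sponsor should weigh that against an estimate that does not depend on r.

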Official Study Title:

Towards the development of a mobile-health technology designed to encourage the use of serious game-based interventions in patients with mild cognitive impairment outside the clinic

NCT Number:

NCT04920123

Document Type:

Study Protocol

Document Date:

February 05, 2025

STUDY PROTOCOL

Study Procedures:

1. [Recruitment](#)
2. [Screening](#)
3. [Informed consent obtainment](#)
4. [Random assignment into two groups](#)
5. [Assessment at baseline](#)
6. [Shipping tablet PC5. Assessment at baseline \(Only Rutgers RA can perform assessment; UMass RAs will organize the overall meeting\)](#)
7. [Tutorial for the intervention group](#)
8. [Checking compliance every week \(twice per week\)](#)
9. [Assessment after 12 weeks](#)
10. Returning tablet PC
11. Focus group (Online workshop)
12. Assessment after 24 weeks

Role Assignment

	UMass RA	Rutgers RA
Recruitment	O	O
Screening	O	O
Informed consent obtainment	O	O
Random assignment into two groups	O	X
Assessment at baseline	O (general instructions before assessment)	O (actual assessment)
Shipping tablet PC	O	X
Tutorial for the intervention group	O	X
Checking compliance every week	O	X
Assessment after 12 weeks	O (general instructions before assessment)	O (actual assessment)
Returning table PC	O	X
Focus group (Online workshop)	O	X
Assessment after 24 weeks	O (general instructions before assessment)	O (actual assessment)

1. Recruitment:

- **50** participants with Mild Cognitive Impairment (MCI) will be recruited as follows.

[figure not shown]
- Currently planned means:
 - Emailing recruitment flyers to residents in local senior centers in Amherst, MA and Union, NJ
 - Emailing recruitment flyers to support groups and conferences
 - Posting recruitment flyers on the Internet (e.g., ClinicalTrials.gov, National Alliance on Mental Illness; nami.org, Alzheimer's Association; alz.org, UMass newsletter)
 - Posting an abbreviated recruiting message + screen shots of flyers on the social media (e.g., Facebook, Twitter)
 - Recruiting message: *"If you believe you have mild cognitive impairment, and are interested in cognitive training using mobile games, please contact AHHA Lab [contact], [contact].)"*
 - Visit senior villages
- Optional means:
 - Using paid third-party services that perform the recruiting process
 - Advertising on local newspapers

- The flyer can be found in [**Appendix 1**](#). (unified phone number / email address)

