	No Access (Hidden)	Read Only	View & Edit																																		
Volunteer Demographics																																					
Screening Data																																					
Screened Result																																					
Informed Consent																																					
Randomization Form																																					
Baseline Data																																					
12-Week Follow-up Data																																					
24-Week Follow-up Data																																					

5. Assessment at baseline (Only Rutgers RA can perform assessment; UMass RAs will organize the overall meeting)

- A UMass RA will remind the participant of the scheduled assessment.
 - Give a call to the participant, remind them 1 day before the scheduled assessment in the following order.
 - Phone call
 - If not answering, text and email.
 - Give a call to the participant, remind them 2 hours before the scheduled assessment.
 - Phone call
 - If not answering, text and email.
- A UMass RA will organize the zoom meeting.
 - The UMass RA will initiate a zoom meeting.
 - A UMass RA will email a zoom link to the participant's email and the Rutgers RA approximately 10 minutes before the scheduled time.
 - The Rutgers RA will join the meeting.
 - Introduce RAs
 - Message: "*Hello, [Participant name]. I am [Umass RA name], and a researcher from UMass Amherst. Today, we will administer cognitive assessments and some surveys to you and your helper. They will take about 2 hours to complete. All the assessments will be administered by [Rutgers RA]. Can you introduce yourself briefly, [Rutgers RA]? Before starting assessments, I will break a room for [Rutgers RA] to give some important instructions for today's session.*
 - The UMass RA will break out a meeting room for the Rutgers RA, and the Rutgers RA will wait in the room.

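### The paired t-test can use only participants with a complete pair, so randomised first-period data from anyone lost after week 12 go unused; the cost is mainly power, and bias depends on why people leave

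*SAP*

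**What the plan says.** SAP section 1 describes the design: "This study uses a two-period crossover design in which Group A and Group B alternate between an intervention and a non-intervention period". Protocol step 1 plans for 50 "participants with Mild Cognitive Impairment (MCI) will be recruited as follows". Under Protocol step 4 a study assistant consults a pre-determined list and "assigns the study ID to either Group A or B"; the allocation ratio is not given. Assessments take place at baseline (step 5), week 12 (step 9: "After 12 weeks, all participants will be assessed with the following tests") and week 24 (step 12).

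SAP section 2 gives the whole analysis: "Paired t-tests will be conducted to evaluate changes in outcome measures between the intervention and non-intervention periods". It adds seven outcomes, the directional hypotheses and the test level: "All analyses will be conducted using Python, with a one-sided significance level of 0.05". The SAP text available for review (sections 1 and 2) and the protocol define neither the paired quantity nor the analysis population. They also give no missing-data rule, expected dropout or sensitivity analysis, and no use for data from a participant who completes only one period.

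**The concern.** Week 12 closes the first period and opens the second. A within-person comparison of the two periods therefore cannot be formed for someone who leaves after week 12. That person has nevertheless supplied a baseline score and a week-12 score under a randomised assignment, so they carry direct evidence on training against control. The chosen test has no place for it. Adding a sentence on missing data would not change this, short of imputation.

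Two things are at stake. The first is precision in a trial of only 50. The second is what the result describes: people who finished a 24-week home programme, rather than the groups as randomised. The groups also face different demands after week 12, since Group A has finished the game and Group B is about to start it. Dropout that differs between groups is therefore plausible, although nothing in the documents shows that it will occur.

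**Working it through.** The plan states no power, effect size, SD or dropout, so there is no figure of its own to reproduce.

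**Inputs from the documents.** 50 participants; two sequences; visits at weeks 0, 12 and 24; paired t-test at one-sided 0.05.

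**Assumed inputs.** 25 per group; score SD 1; equal correlation ρ of 0.6 or 0.8 between any two visits; an effect of 0.40 SD that persists after training stops; dropout after week 12 of 0, 10 or 20%.

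**Step 1: the paired quantity.** If period changes are paired, each person's value is
- Group A: (Y12 − Y0) − (Y24 − Y12) = 2·Y12 − Y0 − Y24
- Group B: (Y24 − Y12) − (Y12 − Y0) = Y24 + Y0 − 2·Y12

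One missing visit removes the value. If end-of-period scores are paired, the value is ±(Y12 − Y24). Baseline is then not needed, but a person without week 24 is still lost.

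**Step 2: precision of the paired test.** The variance of one value is 4 + 1 + 1 − 4ρ − 4ρ + 2ρ = 6(1 − ρ), which is 2.4 at ρ = 0.6 and 1.2 at ρ = 0.8. With n complete pairs, SE = √(6(1 − ρ)/n). Power is from the noncentral t distribution on n − 1 degrees of freedom.

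**Step 3: precision with all visits.** Take a common baseline mean and known covariance. The contrast is (2·A12 − A24 − 2·B12 + B24)/2, where A12 is Group A's mean at week 12, and so on; the baseline terms cancel. Let b = ρ/(1 + ρ), V = (2 − b)²(1 − ρ²) and R = 1 − 2ρ²/(1 + ρ). With m people per group seen at week 24, variance = ½(V/25 + R/m). V and R are 1.690 and 0.550 at ρ = 0.6, and 0.871 and 0.289 at ρ = 0.8. Power is Φ(0.40/SE − 1.645).

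| ρ | Random dropout | Pairs | Paired SE | Paired power | All-visit SE | All-visit power | Gap (points) |
|---|---|---|---|---|---|---|---|
| 0.6 | 0% | 50 | 0.2191 | 56.2% | 0.2117 | 59.7% | 3.5 |
| 0.6 | 10% | 45 | 0.2309 | 52.4% | 0.2145 | 58.7% | 6.3 |
| 0.6 | 20% | 40 | 0.2449 | 48.4% | 0.2181 | 57.5% | 9.1 |
| 0.8 | 0% | 50 | 0.1549 | 81.6% | 0.1523 | 83.7% | 2.1 |
| 0.8 | 10% | 45 | 0.1633 | 77.8% | 0.1544 | 82.8% | 5.0 |
| 0.8 | 20% | 40 | 0.1732 | 73.4% | 0.1570 | 81.7% | 8.3 |

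Simulation in the same setting agrees. At 20% random dropout, paired against all-visit power was 50% against 58% (ρ = 0.6) and 70% against 80% (ρ = 0.8). At 10% it was 51.9% against 56.5% and 77.7% against 82.6%.

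**Step 4: bias, by simulation.**
- *Random dropout:* none. At correlation 0.7 with no true effect, the paired test rejected in 4.5 to 4.9% of trials across 10 to 30% dropout.
- *Poor first-period change drives 20% dropout by the same rule in both groups:* the paired estimate averages 0.37 to 0.39 against a true 0.40. That is low by (0.40 − 0.39)/0.40 = 2.5% to (0.40 − 0.37)/0.40 = 7.5%. Type I error stays near 5%. Losing poor week-12 changes pushes the paired value up in Group A and down in Group B, so the two largely offset.
- *The worst-responding 20% of Group A (5 of 25) leave and nobody else, no true effect:* the paired estimate is +0.13 to +0.19 SD, with about 20% false positives. The all-visit model stays near 0, with 4 to 5%. A separate simulation with score SD 3, correlation 0.7 and individual variation in response gave +0.39 points and 17.1% for the paired test. In a smaller run of that setting with an estimated unstructured covariance, the model gave 0.03 points and 5.5%, against 15.5% for the paired test.

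**The case against.** **Dropout may be small.** The protocol calls participants twice weekly, reminds them one day and two hours before each assessment, and pays $34 per assessment. At 10% dropout the gap is only about 4 to 6 points, of which 2 to 3 would exist anyway. This stands, and it limits the size of the problem.

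**The comparator is flattered.** Steps 2 and 3 treat the covariance as known, whereas 50 people must supply it. Referring the model to a t distribution on 48 degrees of freedom lowers its power at 20% dropout to 56.5% and 80.7%, and the gaps to 8.1 and 7.3 points. A run with an estimated unstructured covariance (correlation 0.7, effect 1 point on SD 3, 20% random dropout) still gave 52.5% against 44.5%, with simulation error of about 2 to 5 points. The 8 to 10 points are best read as the upper part of the plausible range.

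**Stronger readings that the documents do not support.**
- A reader might infer that the SAP prescribes a completers-only analysis. It does not. Exclusion is what the named test implies when no rule is given; imputation before pairing is not ruled out. Python's standard paired test returns no result when values are missing unless told to omit them, so an unplanned analyst choice would decide.
- A reader might infer that the estimate will be biased. Size and direction depend on a dropout mechanism that the documents do not describe.
- A reader might take the whole gap between methods as loss due to dropout. In the table at ρ = 0.6, dropout of 20% takes the paired test from 56.2% to 48.4%; the rest of the 9.1-point gap is the difference in method.
- A reader might infer that unequal dropout lets practice effects through. With assumed practice gains of 0.2 and 0.1 SD, the group means of the paired value are the effect ± 0.1. With 20 against 25 completers the bias is 0.1 × 5/45 = 0.011 SD; with 15 against 25 it is 0.1 × 10/40 = 0.025 SD. That is too small to argue from.

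**Conclusion.** The point holds as an efficiency loss with a conditional risk of bias. On either reading of the paired quantity, anyone without week 24 contributes nothing to the only named analysis, and their randomised week-12 evidence is unused. With 25 per group and a persistent 0.40 SD effect, the cost in power is about 4 to 6 points at 10% random dropout and up to about 8 to 10 at 20%, including the 2 to 3 points present without dropout. Bias ranges from none, through about 3 to 8% towards no effect, to a false-positive rate of about 20% in favour of the game when Group A's worst responders alone leave.

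Dropout rate, mechanism, SD, correlation, effect size and equal allocation are all assumptions, so the harm in this trial cannot be fixed from the documents. The silence on missing data is judged on the text available for review. The change is worth making before the data are analysed, because a better method exists for data already being collected.

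**What to change.** 1. Define the paired quantity: period changes or end-of-period scores.
2. Make the main analysis a linear mixed model of baseline, week-12 and week-24 scores in all randomised participants by assigned group, using every available visit. Include visit as a category, a common baseline mean, group-by-visit terms, and an estimated unstructured covariance (or compound-symmetric).
3. Prespecify the effect as intervention-period change minus non-intervention-period change, averaged over the two sequences: (2·A12 − A24 − 2·B12 + B24)/2, with its confidence interval.
4. Also report the randomised week-12 contrast, A12 − B12. It does not rest on the gain persisting. If an effect e vanished in Group A by week 24, the contrast in item 3 would be (2e + e)/2 = 1.5e.
5. Keep the paired t-test in completers as a sensitivity analysis, and report dropout by group and period.

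The cost is SAP wording and slightly more programming in the Python already named; no new data are needed. The model removes the bias only if data are missing at random given the observed scores. Loss driven by unseen week-24 scores would need a further sensitivity analysis.
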